 - In order to remove all the blood, as well as to obtain clear images, iodinated contrast is infused at a flow rate of 5 mL/s over 4 s, at 400 psi of pressure (Acist, Eden Prairie, Minnesota). Automatic pullback at 20 mm/s.
- If needed, blood samples can be taken through Recover catheter (Hexacath, Rueil-Malmaison, France)
- The same procedure will be performed:
 - o on "healthy" (without ground glass appearance at CT scan) area in the same lung
 - o on contralateral lung, both in "ground glass" and "healthy" areas according to CT scan.

PRIMARY ENDPOINT

- Overall safety of OCT procedure in COVID-19 pneumonia patients
- Presence of microvascular pulmonary thrombosis at OCT assessment in COVID-19 patients, both in "ground glass" and "healthy" ventilated areas.

SECONDARY ENDPOINT

- Pulmonary artery vessel anatomy characterization in COVID-19 patients
- Correlations with single trans-thoracic echocardiography (TTE) pulmonary hypertension (PH, estimated systolic pulmonary artery pressure > 35 mmHg) and right ventricular disfunction (RVD: tricuspid annular plane systolic excursion < 17 mm or Doppler tissue imaging S wave < 9.5 cm/sec).
- Dynamic correlations with standard inflammatory, coagulation and tissue damage

Study design, sample size, statistical analysis

The study is an open label, prospective, interventional clinical study of the safety, tolerability and potential diagnostic value of optical coherence tomography for microvascular lung vessels obstructive thromboinflammatory syndrome assessment in patients with COVID-19 pneumonia. This is a proof of concept exploratory study and will be conducted in 10 patients with mild-to-severe

The sample size calculation was designed for safety assessment based on a reference population of last 100 patients who underwent OCT at our Institution for coronary Artery Disease (CAD) in which a rate of SAEs lower than 1% have been recorded (personal communication)

Primary endpoint

ARDS.

As for safety analysis, the number of imaging related complications (expected/unexpected) and serious events (SAEs) (expected/unexpected and/or related/not related) and the percentage of subjects experiencing imaging related event (IRE) and SAEs in the study will be summarized by severity and within body system involved. Narratives will also be presented.

Secondary endpoints

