- Description of event (if the event consists of a cluster of signs and/or symptoms, record a diagnosis [e.g.: "flu"] rather than each sign and symptom)
- Onset date
- Stop date (if resolved)
- Seriousness (see definition of serious adverse events below)
- Intensity ("Mild" [does not interfere with daily activities]; "Moderate" [interferes with daily activities]; "Severe" [prevents daily activities])
- Relationship to study intervention (Not Related, Possibly Related, Probably Related)
- Action taken (None, Required concomitant treatment, Permanent discontinuation of study intervention, Other [explain])
- Outcome (recovered without sequelae, Resolved with sequelae, Ongoing, Unknown, Death)

Serious Adverse Events (SAE)

An SAE is an AE that meets 1 or more of the following criteria:

- Results in death
- Is immediately life-threatening (places the subject at immediate risk of death from the event as it occurred)
- Requires or prolongs in-patient hospitalization
- Results in a persistent or significant disability or incapacity
- Results in a congenital anomaly or birth defect or malignancy
- Is medically important
- Requires medical intervention to prevent permanent impairment or damage

Imaging-related events

Intra-procedural adverse events will be recorded and considered as potential imaging-related events (IRE). IRE will be defined as the occurrence of clinical symptoms (worsening of respiratory failure, requiring invasive mechanical ventilation, hemoptysis), adverse angiographic outcomes (dissection, perforation, vasospasm, thrombus formation, abrupt closure), requiring interruption of the imaging procedure during intra-polmonary imaging and will be routinely registered by the operator. Major peri-procedural adverse events will be also be recorded: death, acute kidney injury, major bleedings, contrast media reaction, access-site related complications.

Fundings: The procedure will be covered by SSN. The other costs (see attached table of costs) will be covered by COVID BIOB funds.

REFERENCES

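### Does the primary safety summary lose mild OCT complications that neither interrupt imaging nor count as serious?

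*Protocol*

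**What the plan says.** The first primary endpoint is "Overall safety of OCT procedure in COVID-19 pneumonia patients". The section Study design, sample size, statistical analysis describes an "interventional clinical study of the safety, tolerability and potential diagnostic value of optical coherence tomography", to be run in 10 patients.

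Its paragraph on the primary endpoint sets out the safety summary in one sentence with two parts:

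- counts: "the number of imaging related complications (expected/unexpected"), together with the number of serious events, whether or not expected and whether or not related;
- subject percentages: "the percentage of subjects experiencing imaging related event (IRE) and SAEs in the study will be summarized by severity", and also by body system.

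Narratives are added to both.

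The section Imaging-related events begins broadly: "Intra-procedural adverse events will be recorded and considered as potential imaging-related events (IRE"). It then defines an IRE through listed clinical symptoms and "adverse angiographic outcomes (dissection, perforation, vasospasm, thrombus formation, abrupt closure"), with the qualifier "requiring interruption of the imaging procedure during intra-polmonary imaging and will be routinely registered by the operator". A further sentence adds: "Major peri-procedural adverse events will be also be recorded: death, acute kidney injury, major bleedings, contrast media reaction, access-site related complications".

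The section Adverse events (AE) has all AEs recorded throughout the study. Each is classified by seriousness, a three-level intensity scale (mild, moderate, severe) and relationship to the study intervention.

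**The concern.** The two named percentages both have a threshold. An SAE must meet a seriousness criterion, and an IRE, at least an angiographic one, must have made the operator interrupt imaging. A complication below both thresholds moves neither figure. Examples are a short vasospasm during which imaging continues, a mild contrast reaction or a minor access-site problem.

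The study claims to assess tolerability as well as safety, and mild events are what tolerability is about. If the primary result came out as 0% IRE and 0% SAE, a reader might conclude that the procedure had no complications when some patients had minor ones. The error could run in one direction only: the two percentages can miss such events and cannot overcount them. In a study of 10, each missed patient is worth 10 percentage points of an any-complication rate.

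**Working it through.** **1. Does such an event exist under the definitions?** The sentence defining an IRE can be read in two ways: the interruption condition may govern all listed items, or only the angiographic ones.

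| Event, assumed non-serious, imaging continued | IRE, condition on all items | IRE, condition on angiographic items only | SAE | Recorded |
|---|---|---|---|---|
| Brief vasospasm | No | No | No | Yes, as AE |
| Slight haemoptysis | No | Yes | No | Yes, as AE |
| Mild contrast reaction | Not listed | Not listed | No | Yes, as AE and as a named peri-procedural event |
| Minor access-site event | Not listed | Not listed | No | Yes, as AE and as a named peri-procedural event |

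So the class is not empty under either reading, and brief vasospasm is its clearest member. Acute kidney injury is a poor example. The Protocol lists it among major peri-procedural events, and many cases would meet an SAE criterion such as medical importance or prolonged hospital stay.

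**2. Does the plan lose the event?** Three provisions bear on this.

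- Recording: every AE goes on the CRF with seriousness, intensity and relationship. Intra-procedural AEs are also all treated as potential IREs.
- Counting: the safety paragraph names complications separately from IREs. If the two were the same set, the first term would add only a change from events to subjects. The natural reading is that complications is the wider class and IRE the narrower one.
- Presentation: the summary is to be broken down by severity. If severity means the recorded intensity scale, mild events are expected in it. Narratives accompany it.

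Nothing in the paragraph says that only IREs and SAEs may be tabulated.

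**3. What does the missing percentage amount to at N = 10?** One patient is 1/10 = 10 percentage points. Exact (Clopper-Pearson) 95% intervals:

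- 0/10: 0%, upper limit 1 − 0.025^(1/10) = 0.308, so 0 to 30.8%
- 1/10: 10%, 0.3 to 44.5%
- 2/10: 20%, 2.5 to 55.6%

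The chance that at least one of 10 patients has such an event is 1 − (1 − p)^10. The rates p are assumptions, because the Protocol gives none:

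- p = 2%: 1 − 0.98^10 = 18%
- p = 5%: 1 − 0.95^10 = 40%
- p = 10%: 1 − 0.90^10 = 65%
- p = 20%: 1 − 0.80^10 = 89%

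The arithmetic is right, but it would be the same for any proportion in any study of 10. It shows that such an event could well occur. It does not show that this plan would hide it. Since AEs are recorded patient by patient, the number of affected patients can be read off and divided by 10.

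**4. Is the misleading result, 0% IRE and 0% SAE, likely?** SAEs are counted whether or not related to the procedure. Both parts of the inclusion criteria require severe pulmonary COVID-19, and the SAE criteria include death and prolonged hospital stay. An SAE percentage of zero is doubtful in such patients. If it occurred, the complication count and the narratives would stand beside it.

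**The case for a change.** The strongest opposing case is that the count of complications rests on a term the Protocol never defines, while IRE, used in the same sentence, is defined. Read narrowly, complications and IREs coincide, and a brief vasospasm is then left to the AE page and perhaps a narrative. Contrast reactions and access-site events are to be recorded with no summary attached. Mild events are also plausible: each run uses 5 mL/s × 4 s = 20 mL of contrast. Assuming one run in each of four areas (affected and healthy, both lungs), that is 80 mL for OCT alone. The SAE percentage by itself says little about procedural risk, since at a true rate of 1% the chance of seeing any event in 10 patients is 1 − 0.99^10 = 9.6%. A row for patients with any procedural AE would cost almost nothing.

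What stands is that the Protocol fixes no percentage for this class and could have defined complications against IRE. But the first is an additional table of the kind a SAP routinely supplies, and the SAP is not at hand. The second is a loose term that an analyst would resolve sensibly in favour of the wider class, given the opening sentence on potential IREs and the breakdown by severity. That the Protocol does not demand a table is different from its ruling one out. The overlap between thrombus formation as an IRE item and thrombosis as the other primary endpoint is a separate question of classification. It has no bearing on whether mild events are reported.

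**Conclusion.** The concern does not hold. A non-serious event that does not interrupt imaging is indeed outside both named percentages. The plan nevertheless records it, provides a count of complications and narratives in which it can appear, and leaves room for an AE table. No figure or rule in the Protocol is shown to give a wrong result.

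The size of the supposed gap is unknown. Each affected patient would be worth 10 points of an any-complication rate, but how many there would be depends entirely on assumed rates. The conclusion rests on two readings: that complications is the wider class and IRE the narrower one, and that an all-AE table is SAP material. If the first reading failed, the events would still be on the AE page, and what remained would be a matter of reporting detail.
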